3.5 Enrollment of Networks and Randomization

Prospective index participants in networks consisting of one or more eligible network members (either HIV-negative or positive) will be contacted within 60 days of their HIV pre-test counseling visit to learn of their eligibility status. All individuals to be randomized must have initiated screening procedures fewer than 60 days prior to the planned date of randomization. Individuals who exceed this 60-day limit may be re-screened, and all screening procedures must then be completed before their network is qualified for randomization. Index participants will be randomized along with their network member(s) to either the experimental or control arm. Study staff will contact index participants and network members to confirm their enrollment status.

If no prospective network members identified by an index have presented for screening, been found to be eligible, and provided study consent within the 60 days following the index participant's pre-test counseling visit, the index participant will be considered ineligible for the study as a member of that network.

Note: Individuals who initially screen (and provide consent) as an index member may subsequently be screened as a network member for another network, but must first complete the network member informed consent process and member screening assessment. As above, if the time between the participants initial HIV blood draw and enrollment/randomization of the network exceed 60 days, screening procedures as specified in the SSP manual must be repeated.

Note: Individuals who initially screen as a network member may subsequently be screened as a network member for another network, but must first complete the member screening assessment for each network they are screening for. As above, if the time between the participants' initial HIV blood draw and enrollment/randomization of the network for which they qualify exceed 60 days, screening procedures as specified in the SSP manual must be repeated.

Note: Individuals who initially screen as a network member may not screen as an index member for 3 months after their initial blood draw for HIV testing to allow for the dissipation of any

measurement effects. After this three-month period, the individual may undergo the screening procedures as an index member after completing the index screening informed consent process.

3.6 Participant Retention

Once a participant has enrolled in the study, the study site will make every reasonable effort to retain him/her for the duration of the study. Retention rates of at least 90 percent annually are targeted. Study site staff are responsible for developing and implementing local standard operating procedures to achieve this high level of follow-up.

To enhance retention, sites will collect detailed locator information for each participant and will update this information quarterly, develop and implement comprehensive protocols for follow-up, perform field visits when participants are unable to come to the local sites for visits, and implement remote access protocols, when feasible, for participants who move away from study sites. Examples of procedures to enhance participation in the intervention phase and retention during the follow-up phase will include any of the following as locally appropriate:

- Collection of complete locator information
- Use of appointment cards
- Dissemination of thank-you letters after enrollment
- Use of self-addressed postcards for notification of address changes
- Reminder letters and calls before appointments
- Immediate multi-faceted follow-up on missed visits, including calls, letters and home visits
- Searches of local resources to locate participant (e.g. post office check)

3.7 Participant Withdrawal

Participants may withdraw from the study for any reason at any time. The investigator also may withdraw participants from the study in order to protect their safety and/or if they are unwilling or unable to comply with required study procedures. See Section 5.6 for assessments to be performed if possible for participants who withdraw. Participants also may be withdrawn if the sponsor or regulatory authorities terminate the study prior to its planned end date. Indexes who do not complete the peer education training will continue in the study and will complete all follow-up visits as scheduled, as will their network members.

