5.6 Study Endpoint Assessment for Participants Who Withdraw

Participants who withdraw from the study (see Section 3.7) will be asked to participate in an endof-study assessment of their HIV status. In the last six months of the study, site staff will initiate contact with these participants who withdrew from the study, and they will be asked to undergo HIV counseling and testing only.

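### Section 3.7 permits investigators to withdraw participants from follow-up for non-compliance, which conflicts with Section 3.6 and risks avoidable informative censoring

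*Protocol*

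**What the plan says.** Four parts of the protocol bear on this.

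- **Section 3.7, investigator withdrawal.** Besides a separate safety ground, the investigator has the power to take people out of the trial "if they are unwilling or unable to comply with required study procedures". The power is discretionary. The protocol does not say how much non-compliance is enough or which procedures count.
- **Section 3.7, last sentence.** "Indexes who do not complete the peer education training will continue in the study and will complete all follow-up visits as scheduled", and the same holds for their network members.
- **Section 3.6.** Once a participant is enrolled, "the study site will make every reasonable effort to retain him/her for the duration of the study". The target is at least 90% retention per year. The listed means include field visits, remote access for people who move, and immediate follow-up of missed visits.
- **Sections 3.7 and 5.6, after withdrawal.** Section 3.7 points ahead: "See Section 5.6 for assessments to be performed if possible for participants who withdraw". Under Section 5.6 these people "will be asked to participate in an endof-study assessment of their HIV status". The timing is late: "In the last six months of the study, site staff will initiate contact with these participants who withdrew from the study". Only HIV counseling and testing is offered.

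Participants who stay in follow-up have visits with surveys and, if HIV-uninfected, HIV tests every six months (Section 5.3). The primary analysis is a marginal Cox model stratified by site (Section 7.5.1).

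**The concern.** Sections 3.6 and 3.7 pull in opposite directions. Faced with the same poorly attending participant, one site could pursue home visits under 3.6 and another could withdraw the person under 3.7. Both would be following the protocol.

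The Cox analysis treats censoring as unrelated to the risk of infection. Among people who inject drugs, poor attendance may well go with higher HIV risk. If so, ending scheduled testing by site decision makes the censoring informative. It also ends the six-monthly surveys that supply the secondary endpoints. An analysis plan cannot recover tests and surveys that were never done.

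The intervention is open, and blinding is stated only for the behavioral survey interviewers (Sections 2.3 and 5.3). It is a fair inference, though not a statement in the protocol, that whoever decides on withdrawal may know the arm.

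**Working it through.** **1. What the safeguard in 3.7 covers**

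| Form of non-compliance | Who can show it | Protected by the last sentence of 3.7? |
|---|---|---|
| Training sessions not completed | Experimental indexes | Yes, with their network members |
| Booster at 6 or 12 months missed | Experimental indexes | Not named (boosters have their own Section 4.1.2 and their own row in the Appendix II table) |
| Visits, surveys, counseling or tests missed | Everyone, both arms | Not named |

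The only arm-specific gap left is the boosters. The other gaps are common to both arms.

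**2. What remains after withdrawal**

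The study lasts about 48 months, enrollment about 30, and individual follow-up at most 30 (Section 2.3). The Section 5.6 contact therefore starts at about month 48 − 6 = 42. Anyone enrolled before month 42 − 30 = 12 has by then passed their own 30-month maximum. With even accrual (an assumption) that is 12/30 = 40% of participants. A positive result in one of them could not be placed inside their follow-up, whereas six-monthly tests would have dated it.

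**3. The protocol's own sample size**

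Inputs from Section 7.3.1: P_E = 0.071, P_C = 0.116, n = 2.5, κ = 0.2, two-sided α = 0.05, power 90%.

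T = (1.960 + 1.282)² × (0.071 × 0.929 + 0.116 × 0.884) × (1 + 1.5 × 0.2) / 0.045² ≈ 1137 per arm, or 1137/2.5 ≈ 455 networks.

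The protocol states 1112 and 445. The gap of about 2% is rounding: P_E = 0.0705 gives 1109 and 444. The sample size is not in question here. It supplies the inputs for step 5.

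**4. One-sided worst case under the design effect**

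Assumptions, none of them from the protocol: a share p of the experimental arm, with h times the hazard of the rest of that arm, is withdrawn soon after randomization; no control is withdrawn; no endpoint is retrieved. The average hazard of the arm is (1 − p + p·h) times that of those who remain, so

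apparent HR ≈ 0.60 / (1 − p + p·h)

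| p | h = 1 | h = 2 | h = 3 |
|---|---|---|---|
| 5% | 0.600 | 0.60/1.05 = 0.571 | 0.60/1.10 = 0.545 |
| 10% | 0.600 | 0.60/1.10 = 0.545 | 0.60/1.20 = 0.500 |

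**5. The same worst case with no true effect**

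Seroconversion is 11.6% in both arms, with 1112 per arm before withdrawals, design effect 1.3 and a normal approximation.

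| p | Apparent risk ratio, h = 2 to 3 | Two-sided type I error, h = 2 to 3 |
|---|---|---|
| 2% | 0.98 to 0.96 | 5.3% to 6.0% |
| 5% | 0.95 to 0.91 | 6.5% to 10.6% |
| 10% | 0.91 to 0.83 | 10.4% to 24.4% |

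With h = 1 there is no bias at any p. Balanced withdrawal or retrieval under Section 5.6 shrinks all of these figures.

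**The case against.** A reader might infer that Section 3.7 has unblinded investigators removing poor compliers, and that this tilts the trial toward the intervention. The protocol does not support that reading.

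- The clause says the investigator may withdraw, not must, and it sits beside a strong retention duty.
- The six training sessions are most of the difference in procedures between arms, and failing to complete them is expressly not a reason to leave follow-up.
- Section 4.1.2 foresees missed boosters through its 60-day window and attaches no withdrawal to them. Section 5.3 treats out-of-window visits as interim visits.
- Network members have the same scheduled procedures in both arms. Indexes are 1 of 2.5 HIV-uninfected people per network, or 40%. If boosters alone drove the excess, losing 5% of the experimental arm would mean withdrawing 5%/0.40 = 12.5% of its indexes. Nothing in the protocol suggests such a rate.
- Extra contact in the experimental arm could equally improve retention there. Some of these people would be lost anyway, and the sample size already allows 10% loss per year.
- Section 5.6 refers back to 3.7 as a whole, so it can be read to cover investigator withdrawals. The Study Monitoring Committee also watches retention (Section 7.6).

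Most of this stands, and it limits the point to a gap in wording. It does not remove the conflict between 3.6 and 3.7 or the loss of scheduled tests and surveys once the power is used. Nor does it settle the scope of 5.6, because both sections speak of participants who withdraw, not of those whom the investigator withdraws.

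**Conclusion.** The point holds as a narrow but real flaw. Section 3.7 gives an open-ended, discretionary ground for ending follow-up that conflicts with Section 3.6. Using it replaces six-monthly testing with at most one late test and stops the surveys. If such withdrawals are related to HIV risk, the result is avoidable informative censoring in the primary analysis and lost secondary data.

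Neither size nor direction can be derived from the protocol, which gives no withdrawal rate by cause or arm. The shift from 0.60 to about 0.57 to 0.55 at 5% withdrawn is an upper illustration. It requires one-sided, early withdrawal of people at 2 to 3 times the hazard of the rest of their arm, and no retrieval. Balanced withdrawal mainly costs person-time. The change is worth making because it is cheap and extends a principle that 3.7 already applies to the training.

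**What to change.** - **Section 3.7:** remove non-compliance as a ground for investigator withdrawal from follow-up. State that participants in either arm and either role who miss or decline sessions, boosters, visits or other procedures stay on the six-monthly HIV testing and survey schedule that applies to them, unless they themselves decline further contact. Leave the safety and study-termination grounds, and the participant's own right to withdraw, unchanged.
- **Section 5.6:** state that it also covers participants withdrawn by the investigator.

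The cost is a wording amendment. Sites would keep some poorly attending participants on their contact lists, which Section 3.6 already requires.

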4.0 BEHAVIORAL INTERVENTIONS

4.1 Experimental Peer Education Intervention

The experimental intervention is a cognitive-behavioral and social influence peer educator training program comprised of theory-based exercises and activities, and outreach training. The intervention addresses knowledge, attitudes, intentions, and social influences aimed at reducing sexual and drug risk practices among the participants and their network members. As networks are important sources of informational, emotional, and material support across cultures, it is anticipated that this intervention will be appropriate across a range of cultures. It is expected that the program will be adapted to individual contexts and cultures but retain comparability across sites and cultures.

The intervention will be delivered in six two-hour sessions by two facilitators to groups with a maximum of 12 index participants, as described below. These sessions will occur within a four-week time frame and will focus on skills building and practicing promotion of HIV prevention messages among the indexes' network members. The first four sessions will be offered in the first two weeks, and the final two sessions will occur in Weeks 3 and 4. The 4-week course of the intervention should afford participants opportunities to rehearse their newly acquired peer education skills with the members of their risk networks and to share some of their experiences with other members of their peer-education training group. During the training sessions, experimental group index participants will be encouraged to apply their newly acquired skills with the members of their risk networks. Every effort will be made to maintain a stable group membership for the duration of the peer educator training intervention, but it will not be necessary to maintain the same membership for participation in the booster sessions.

The focus of the intervention will be to encourage outreach and peer education within the index participants' personal risk networks. Goal setting activities in the intervention sessions will be focused on promoting HIV prevention among the network members enrolled in the study; however, index participants also will be encouraged to disseminate prevention information to non-study participant members of their networks. As the intervention is focused within the network, the risk of contamination due to possible interactions between experimental group index participants and control group network members is expected to be small. Nonetheless, as described in Section 7.3.4, the expected intervention effect has been adjusted to account for this.

Prior studies have suggested that contamination is unlikely to pose a major threat to study validity, largely because the social networks of IDUs tend to be naturally structured so that there would be a decreased opportunity for interaction and overlap of network members assigned to the experimental arm versus the control arm. Data from injectors in Baltimore, Philadelphia, and Northern Thailand suggest that HIV risk networks among injectors tend to be small. In the SHIELD study of 804 injectors, the average number of risk network members was five, with a mean relationship duration of 17 years and a median of 12 years. Prior research also suggests that HIV and HIV prevention is not a common topic of spontaneous conversation among injecting populations, which would also decrease the likelihood of contamination across study arms.

The only control group activities will be to contact the index members to inform them of their group assignment and to set up next scheduled appointments. However, sites may elect to hold focus groups with some of the control group indexes provided they have IRB approval.

The intervention is designed to promote the dissemination of outreach-related materials and information to the members of the index participants' social networks. One training module component focuses on the indexes specifically tailoring and rehearsing their outreach efforts to their specific network members. Impediments to talking to these specific individuals will be assessed during the intervention sessions, and indexes will be trained in strategies to overcome these impediments.

Efforts will also be made to assess the exposure of study participants to HIV prevention-related messages and materials and to ascertain the sources of this information. Included in the follow-up surveys will be detailed questions about whom participants talked to about HIV, about the HIV prevention materials they received, and about the sources of those materials. Participants will also be tested on their level of recognition of various components affiliated with the experimental arm intervention. This information should help assess the extent to which control arm participants were exposed to elements of the experimental arm intervention.

Group facilitators will follow a detailed intervention manual covering specific topics and activities conducted at each of the peer education sessions. A basic description of each of the sessions is provided below. The site supervisor will perform quality assurance reviews on 10% of the education sessions via direct observation or audiotape. The sessions will be evaluated based on the session length, completion of the intervention components, and impressions of the quality of the delivery by the study site supervisor.

Session 1: Introduction: Participants will be introduced to study goals and will establish group rules in order to build group cohesion. They will discuss ways HIV is transmitted and the role of a peer mentor in disseminating harm reduction messages.

Session 2: Peer Mentoring and Injection-related HIV Risk Behaviors: This session will teach the basic concepts of harm reduction with safer injection behaviors, and how mentors can deliver these concepts within their social networks. Participants will view a video and practice with role-plays.

Session 3: Safer Sex Practices and Communication Skills: This session will motivate participants to adopt less risky sexual behavior. Participants will view a video and practice condom skills.

Session 4: Personal Resistance to Change: Participants will identify their own personal barriers to adopting safer behavior and learn negotiation skills in reducing sexual and injection risk. The session includes training in Active Listening skills.

Session 5: Interpersonal Barriers to Peer Mentoring: During this session, participants will identify and re-frame their barriers to peer mentoring and will practice effective ways to approach others as a peer mentor.

Session 6: Review, Mentor Plans, and Graduation: Participants will set goals for their roles as mentors and will review lessons about harm reduction. There will be a graduation ceremony and refreshments.

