1.1.1 Social Influence and Behavior Change

Social influence processes can have powerful effects on behavior and present an important avenue for HIV prevention research. There is extensive literature on the role of social influence in behavior change.¹¹ Peers may influence each other's sexual behaviors through social comparison processes, fear of social sanctions, information exchange, socialization of new group members, modeling and reinforcement, and social interactions that provide opportunities to meet new sex partners.^{12,13} Some HIV behavior change models include social influence components.^{14,15} The community-wide HIV risk reduction observed among gay men in San Francisco suggests that social influence can be an important approach to behavioral risk reduction.¹⁶ In a study of behavior change among injection drug users in four countries (Brazil, Thailand, Scotland, and the U.S.), Des Jarlais and colleagues found that talking about AIDS with drug-using friends was consistently associated with reduction in self-reported injection and sexual risk behaviors.¹⁷

One social influence strategy that has been widely applied in HIV prevention interventions is outreach. Outreach programs are designed to access "hard-to-reach populations," such as IDUs and their sexual partners, who might not otherwise be exposed to interventions.¹⁸ IDUs in San Francisco reported that outreach workers were their most frequent source of information on bleach for disinfecting needles.¹⁹ Several studies suggest that street outreach is effective in reducing IDUs' risk behaviors.^{20,21} Actively involving individuals from the target population in HIV outreach and education activities can significantly reduce their risk behaviors. One study found that women who discussed risk reduction with friends and neighbors reported significant long-term sexual risk reduction.²² Kelly and colleagues found similar results using this approach with the chronically mentally ill.²³

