2.2 Secondary Objectives

- 1. To determine whether the intervention reduces reported injection and sexual HIV risk behaviors in index participants and/or network members
- 2. To determine whether the intervention changes substance use network norms for injection and sexual HIV risk practices
- 3. To determine whether the intervention effects on injection and sexual HIV risk behaviors differ between index and network participants, or by HIV status in each study arm
- 4. To determine whether the intervention effect on behaviors identified as important mediators of the intervention is similar at both sites

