7.0 STATISTICAL CONSIDERATIONS

7.1 General Design

This is a phase III, multi-site, two-arm, randomized, controlled study of a network-oriented peereducation training intervention for prevention of HIV infection through reduction of HIV risk behaviors among HIV-uninfected IDUs and members of their HIV risk networks. All participants in the study will receive enhanced HIV counseling and testing at screening and semiannually during follow-up. Indexes in the intervention arm receive a six-session peer education training intervention, plus a booster session at six and 12 months, with a maximum of 12 indexes. Indexes in the control arm receive no additional training. Primary and secondary endpoints will be measured on each participant - indexes and network members - every six months for a maximum of 30 months.

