7.3.4 Issues in Sample Size Computation

It is possible that indexes or network members assigned to the experimental group will interact with those assigned to the control. This may attenuate the differences between networks and lead to an underestimation of the effect of the intervention. To take this in account, the study has been powered to detect a decrease of 40% (i.e. a relative risk of 0.6), even though in the SHIELD study, unadjusted OR in excess of 2.0 and adjusted OR as high as 3.0 were observed in behavior change. See Section 4.1 for additional information regarding the possibility of contamination.

The seroincidence rate and the average number of network members will be monitored closely during the study to assure that adequate power is attained.

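### Section 4.1 lets each site hold focus groups with some control-arm indexes, with no limit on topic or timing and no attendance record, so the control condition is loosely fixed and can differ by site

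*Protocol*

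**What the plan says.** Section 4.1 first defines what happens in the control arm: "The only control group activities will be to contact the index members to inform them of their group assignment" and to set up the next appointments. The following sentence opens an exception: "sites may elect to hold focus groups with some of the control group indexes provided they have IRB approval". The protocol says nothing further about these groups.

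Elsewhere the control arm is described without them. The Protocol Summary lists enhanced HIV counseling and testing only. Section 7.1 states: "Indexes in the control arm receive no additional training".

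The experimental arm also works through small groups. Section 4.1 says: "The intervention will be delivered in six two-hour sessions by two facilitators to groups with a maximum of 12 index participants". Booster sessions follow after months 6 and 12.

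Contamination is treated in Section 7.3.4, where the route named is contact between arms: "It is possible that indexes or network members assigned to the experimental group will interact with those assigned to the control". The target effect of a 40% reduction is said to take this into account.

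**The concern.** The exception permits a contact that exists in one arm only, is chosen site by site, and has no stated content. Three places in the protocol suggest that such contact need not be neutral:

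- Section 1.1.1 reports that "talking about AIDS with drug-using friends was consistently associated with reduction in self-reported injection and sexual risk behaviors".
- Section 4.1 argues that contamination is unlikely partly because injectors seldom raise HIV prevention spontaneously. A focus group on that subject would raise it.
- Section 3.5 makes a person screened as a network member wait three months before screening as an index, so that measurement effects can fade. The protocol thus accepts that study contact alone can leave a trace.

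At stake is the meaning of the control arm. Section 7.3.2 concedes that HIV incidence cannot be used to judge the intervention in Philadelphia, so that site is evaluated on self-reported behavior in about 150 networks per arm. Section 2.3 rests the claim of effectiveness in different settings on behavioral mediators, and secondary objective 4 is "To determine whether the intervention effect on behaviors identified as important mediators of the intervention is similar at both sites". If one site runs focus groups and the other does not, a difference between sites in the intervention effect could partly be a difference in the control condition.

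**Working it through.** **Inputs from the protocol (Section 7.3.1 and Table 1).** Average seroconversion probabilities P_E = 0.071 and P_C = 0.116; n = 2.5 HIV-uninfected people per network; κ = 0.2; two-sided α = 0.05; power 90%; 445 networks per arm.

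**Step 1: reproduce the plan's figure.** The Section 7.3 formula is T = (Z_α + Z_β)² [P_E(1−P_E) + P_C(1−P_C)] [1 + (n−1)κ] / (P_E − P_C)².

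- (1.960 + 1.282)² = 10.507
- 0.071×0.929 + 0.116×0.884 = 0.1685
- 1 + 1.5×0.2 = 1.3
- T = 10.507 × 0.1685 × 1.3 / 0.045² ≈ 1,137 per arm, and 1,137/2.5 ≈ 455 networks

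Table 1 prints 1,112 and 445. The gap is 2.2%, plausibly from rounding of the printed probabilities. At 445 networks the effective number per arm is 445×2.5/1.3 = 855.8, the standard error is √(0.1685/855.8) = 0.01403, and power is Φ(0.045/0.01403 − 1.960) = 89.4%.

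**Step 2: dilution of the primary endpoint.** Let f be the share of control networks whose index attends a group, and g the fraction of the full intervention effect that such a network gains. The protocol gives neither, so both are assumptions. The control probability becomes P_C − f·g·(P_C − P_E).

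| f·g | Diluted P_C | Power at 445 networks per arm | Networks per arm for 90% power |
|---|---|---|---|
| 0 | 0.1160 | 89.4% | 455 |
| 1% | 0.1156 | 88.8% | 463 |
| 2.5% (e.g. f = 10%, g = 25%) | 0.1149 | 88.0% | 476 |
| 3% | 0.1147 | 87.7% | 481 |
| 6.25% (f = g = 25%) | 0.1132 | 85.7% | 511 |
| 12.5% (f = 25%, g = 50%) | 0.1104 | 81.1% | 579 |
| 25% (f = g = 50%) | 0.1048 | 69.5% | 767 |

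**Step 3: behavioral endpoint in Philadelphia.** Take the Table 2 row with 40% against 50%, κ = 0.2, cluster size 12 and 90% power. The formula gives 10.507 × (0.24 + 0.25) × (1 + 11×0.2) / 0.10² / 12 = 137.3, so 138, as printed. About 150 networks per arm are planned there. Dilution by f·g moves the control proportion from 0.50 to 0.50 − 0.10·f·g:

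- f·g = 1%: 141 networks
- f·g = 2.5%: 145 networks
- f·g = 4.3%: 150 networks, so the margin in this row is used up
- f·g = 10% (for example three groups of ten, 30 of 150 indexes, with half the effect): difference 9 points, 170 networks

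Other rows of Table 2 have more or less room; at κ = 0.3 the same contrast already needs 185.

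**Step 4: do existing provisions cover it?** The Section 7.3.4 allowance names only interaction between arms. The supervisor's 10% quality review in Section 4.1 is of the education sessions. Follow-up surveys (Sections 2.3, 4.1 and 5.3) ask about exposure to prevention messages and their sources, and could catch some of it. The protocol does not ask for focus-group attendance to be recorded.

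**The case against.** The strongest reply is that nothing here is contradictory and no harm is shown. The focus-group sentence is an express exception to the one before it, so the control condition cannot be said to exclude the groups. Section 7.1 rules out further training, and the protocol nowhere calls a focus group training. The experimental intervention is defined by content (role-plays, videos, condom and negotiation skills, mentor plans), and sharing a group format is not sharing that content. The association in Section 1.1.1 concerns talk among friends, not a staff-run meeting on an unstated topic. Only some indexes are involved, and network members, about 1.5 of the 2.5 HIV-uninfected people per network, are not mentioned. Control participants already receive risk-reduction counseling at screening and every six months (Sections 4.2 and 5.3). The surveys, and the exposure marker listed in Section 7.2.4.2, would catch part of any leakage. The procedures manual, which is not at hand, may add detail.

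Most of this stands. A reader might infer that the groups pull the arm difference toward zero, or that power drops to 81% or 70%. The protocol supports neither. The first needs prevention content that is nowhere described. The second needs a focus group to carry half the effect of six two-hour sessions and two boosters, in a quarter to half of the control networks. Nor does the protocol say that the groups fall within follow-up; it sets no timing at all.

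The reply does not explain why an activity of unstated content should be open to one arm, at each site's choice, when the protocol elsewhere guards against effects of contact alone. IRB approval protects participants; it does not protect the comparison.

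**Conclusion.** The point holds as a loosely fixed control condition, not as a demonstrated bias. The text permits a one-arm, site-elective group contact that the control descriptions and the contamination allowance leave out. Dilution is possible if the groups touch on HIV risk; its size is unknown and may be zero (with g = 0 nothing changes).

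For the primary endpoint, modest assumptions (f·g of 1% to 3%) cost about 0.6 to 1.7 points of power from 89.4%. The behavioral comparisons are more exposed: the Philadelphia evaluation depends on them, one planning row has room for only about 4% dilution, and objective 4 compares sites whose control conditions could differ. The objective 4 problem is doubly conditional: the sites must use the option differently, and the groups must change behavior. Because the exposure is avoidable at almost no cost, a change to the text is worth making.

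**What to change.** In Section 4.1, allow a control index to join a focus group only after that index's network has completed its last scheduled follow-up visit, or delete the sentence. The network's last visit is the right marker because network members also contribute endpoints, and Section 5.3 gives the whole network one Day 0.

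For any group already held, record attendance by index, with date and site, so that a sensitivity analysis can identify the exposed control networks. That analysis can only be supportive: attendance is not randomized, so setting those networks aside would break the randomized comparison. For this reason deferral is better than logging alone.

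The cost is one sentence in Section 4.1 and a simple log. Qualitative feedback from control indexes is delayed or lost, and no endpoint in Section 7.2 uses it. The sample size of 445 networks per arm is unaffected.
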